2.7 QUALITY CONTROL, ASSURANCE, AND CONFIDENTIALITY

2.7.1 Protocol Compliance

The participating site investigators will not intentionally deviate from the protocol for any reason without prior written approval from the IRB, except in when the safety of the research participant is at risk. In that event, the site investigator will notify the IDE Sponsor and the reviewing IRB immediately, if possible, and request approval of the protocol deviation. If prospective IDE Sponsor and IRB approval is not possible, the site investigator will notify the IDE Sponsor and reviewing IRB promptly following the respective protocol deviation. The site investigator will inform the reviewing IRB of all protocol deviations and unanticipated events involving risks to the research subjects and others and will obtain prospective IRB approval for all proposed protocol changes. Persistent or serious noncompliance may result in termination of the site's participation in the clinical trial.

2.7.2 Protocol Deviations and unexpected problems:

Successful implementation of the trial will depend on the protocol being carried out as intended. Sites will be expected to closely monitor activities at the level of the patient, EMS agency and site, report protocol deviations promptly using the electronic data management system, and take necessary actions (including retraining), as appropriate, to bring about a resolution and/or prevent a recurrence. The CCC and DCC, meanwhile, will be tracking activities at the trial level. Serious deviations will be discussed with the other investigators, the DOD, and the FDA to see if the protocol needs to be amended or recruitment put on hold.

2.7.3 Privacy and Confidentiality:

The site investigators and members of their research teams will make a reasonable effort to ensure the confidentiality of research subjects. Subjects' names and other identifiable information will be kept in a secure, locked, limited access area separate from the electronic data management system.

2.7.4 Investigator Responsibilities

The site investigators will agree to implement the IRB approved protocol and to conduct the trial in accordance with 21 CFR Part 812, Subpart E, and the ICH GCP Guidelines (E6, Section 5), as well as with all applicable national, state and local laws. The trial will be performed in accordance with ethical principles that have their origin in the Declaration of Helsinki and are consistent with ICH / Good Clinical Practice, and with applicable regulatory requirements.

3. HUMAN SUBJECTS

TO 0005 PACT will be conducted under the federal provisions governing Exception from the Requirement for Informed Consent for Emergency Research (21 CFR 50.24), including community consultation, public notification, and the notification of participants or their legally authorized representative as soon as feasible after enrollment. Notification may be through oral and/or written communication and will include the opportunity to opt out from ongoing participation.

Community consultation as determined by the IRB will be undertaken prior to final IRB approval. Because the population eligible for enrollment includes all citizens in the trial regions, it will not be possible

to target any particular small group. Feedback from the community regarding any concerns they may have about potential enrollment will be obtained by research personnel. Public notification and community consultation, as directed by the IRB, may include the use of electronic surveys, ads in local media outlets and on public transportation, and/or consultation with community leaders. Due to their ongoing participation in numerous multicenter research studies involving emergency research, the institutions participating in PACT have significant experience with community consultation and notification practices.

3.1 SUBJECT POPULATION

TO 0005 PACT will include prehospital patients who are experiencing traumatic injury, require advanced airway management, and are receiving care from participating EMS agencies. The trial will include only EMS agencies with personnel capable of performing advanced airway management including ETI and SGA placement.

3.2 INCLUSION CRITERIA

1. Traumatic injury requiring advanced airway management. Indicators of the need for advanced airway management include: a) GCS < 8, b) SpO₂ < 90 despite supplemental oxygen, c) ETCO₂ > 60 despite supplemental ventilation, or d) provider discretion.
2. Transport (or intended transport) to an enrolling LITES Trauma Center

3.3 EXCLUSION CRITERIA

1. <15 years of age
2. Pregnancy
3. Prisoner
4. Initial advanced airway attempted by a non-PACT provider
5. Cardiac arrest without ROSC at time of intervention
6. Caustic substance ingestion
7. Airway burns
8. Objection to study voiced by subject or family member at the scene

Inclusion and exclusion criteria will be assessed based on information available at the time of enrollment, defined as the time on scene by the Enrolling EMS Agency. Although all reasonable efforts will be made by the emergency medical crew to either directly witness or obtain documentation of eligibility criteria, due to the nature of the emergency prehospital setting, there may be occasions where the emergency medical crew must rely on verbal report of eligibility criteria from referring hospital or emergency crew. In these instances, if, after subsequent review of outside hospital and/or ground crew documentation, it is determined that the subject did not meet eligibility criteria, the subject will remain enrolled in the study based on the intention-to-treat principle but the incident will be reported as a protocol deviation and the patient will be excluded from the per protocol group for the purpose of analysis.

All patients are prospectively enrolled. The interventions, including standard care, are completed prior to arrival at the hospital. Any patient not identified as an enrollment at the time of treatment will be a missed enrollment. After the interventions are applied, the medical director, who is ultimately responsible for enrollment, will confirm the patient met all inclusions and none of the exclusion criteria. A grace period of three business days is allowed for clarification of an enrollment for those instances where incomplete or conflicting information is provided. If this occurs, documentation in the form of email communication or an addendum to the chart by the crew member will be used to clarify the intent of enrollment by the EMS clinician.

If a verbal report must be used in lieu of physical documentation or directly witnessing eligibility criteria, documentation of the verbal report will serve as the source documentation for determining eligibility. Verbal reports will be documented outlining the source as well as the details.

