In addition to their speed and ease of use, SGAs can be placed blindly without the need for the additional equipment required for a laryngoscopy. In tactical situations, blind insertion techniques may limit tactical exposure and improve light discipline¹⁴. SGAs have been associated with shorter prehospital scene times, which may translate into reduced risk for the provider and decreased patient mortality. Use of SGAs may also be a less perishable skill than the use of ETI, allowing for better retention and faster pre-deployment training.

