2.5 STUDY ENDPOINTS

Primary Outcome: The primary outcome for the trial is 24-hour survival.

Secondary Outcomes: Secondary outcomes include survival to hospital discharge, expected clinical events (including incorrect placement of the airway, inadequate ventilation, airway trauma, or concern for aspiration as defined as documented vomiting and/or need for suctioning), airway management performance (including initial pass success, overall success, and use of rescue technique), ICU length of stay, ventilator days, and expected adverse events including airway trauma, pneumothorax, incidence of acute respiratory distress syndrome (ARDS) and incidence of ventilator associated pneumonia (VAP).

Primary Outcome Definition:

24-hour Mortality: A binary variable defined as death within 24 hours

Secondary Outcome Definitions:

Secondary outcomes will be assessed from arrival at the trauma center through day 30 or discharge, whichever is first.

In-Hospital Mortality: A binary variable defined as death recorded any time after hospital arrival.

Airway Management Performance: The elements of airway management performance include airway misplacement (including endotracheal tube misplacement), initial pass success (the successful placement of device on the first attempt past the teeth confirmed by EtCO₂), sequence of airway insertion, airway insertion success and time, number of airway insertion attempts, inadequate ventilation, and any instances of airway conversion (change of airway in the first 24 hours).

Acute Respiratory Distress Syndrome (ARDS): The Berlin definition for mild ARDS ($\text{PaO}_2/\text{FIO}_2 \leq 300$ mm Hg plus timing, imaging, and origin criteria) will be utilized as a threshold value to determine the incidence of ARDS within 24 hours of presentation. We will further stratify patients into mild, moderate ($\text{PaO}_2/\text{FIO}_2 \leq 200$ mm Hg), or severe ($\text{PaO}_2/\text{FIO}_2 \leq 100$ mm Hg) ARDS.¹⁶

ICU length of stay (LOS): Defined as the number of days spent admitted to the Intensive Care Unit. ICU LOS will be recorded to the first decimal place.

Ventilator Days: Defined as number of days on a mechanical ventilator. Ventilator days will be recorded to the first decimal place.

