2.6.2 Sample Size Determination

This stepped wedge randomized control trial will use 24-hour mortality as its primary outcome to power the trial. This sample size was calculated using the formula presented by Hemming and Taljaard and takes into account the design feature that airway management strategy will be switched from standard care to initial SGA sequentially by 17 prehospital agencies over 7 time periods (6 steps).¹⁷ The intra-randomization unit correlation coefficient (ICC) for the primary outcome was assumed to be 0.025 based on preliminary data from Pittsburgh's prehospital agencies. To detect a decrease from 16.7% to 9.7% (a difference of 7%), with 80% power at 5% significance level, a sample size of 1,904 will be required. To account for 5% dropout, we will need to enroll 118 participants from each of the 17 prehospital agencies over the seven enrollment periods (17 participants per agency per period). Therefore, the total required sample size is 2,006, however, to enroll equal numbers of patients in each enrollment period, we will enroll 2,009 patients.

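### Trial entry can be settled after the arm is known, on two different clocks and past the 24-hour endpoint, so selection bias in the primary comparison cannot be excluded

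*Combined protocol and SAP*

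**What the plan says.** All references are to the combined protocol and SAP.

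- **Assignment.** Agencies step from standard care to initial SGA without blinding (2.1.1). A patient takes whichever arm is active at the treating agency (5.1).
- **First clock.** Section 3.3 bases eligibility on "information available at the time of enrollment, defined as the time on scene by the Enrolling EMS Agency".
- **Second clock.** Exclusion 5 in the same section reads "Cardiac arrest without ROSC at time of intervention".
- **Later confirmation.** The medical director confirms eligibility after treatment. Where information is incomplete or conflicting, "A grace period of three business days is allowed for clarification of an enrollment". An email or chart addendum from the crew then serves as evidence of whether the crew meant to enrol (3.3).
- **Safeguards.** "Any patient not identified as an enrollment at the time of treatment will be a missed enrollment" (3.3). Patients treated with intent to enrol and later found ineligible stay in the intention-to-treat analysis (2.6.4; 3.3 for eligibility taken on verbal report). Patients in whom no advanced airway could be placed are also kept (2.2).
- **Discretion.** The need for an airway may rest on three physiological indicators "or d) provider discretion" (3.2).
- **Endpoint.** "24-hour Mortality: A binary variable defined as death within 24 hours" (2.5).

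**The concern.** When clusters hold a known arm and patients are identified afterwards, the arms stay comparable only if the same kinds of patient enter under each. Two features of section 3.3 leave that open.

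First, arrest status can change between arrival on scene and the airway attempt. If that interval differs by arm, patients at very high risk of death are excluded, or admitted after return of circulation, at different rates.

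Second, an unclear enrolment can be settled by unblinded staff after the 24-hour outcome may be knowable. The evidence is a retrospective account of intent.

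Patients who are never counted cannot be restored by the mixed model in 2.6.1. Because they are likely to have high mortality, small numbers could move the primary endpoint.

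**Working it through.** **Step 1: set the passages side by side.**

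- The two clocks are not merely loose wording. Subgroup 9 in 2.6.3 consists of patients in arrest at enrolment who then regained circulation. The plan therefore expects arrest status to change between the two times and admits those who recover.
- Section 2.2 keeps patients when preparation or placement fails. It does not say whether someone who arrests during preparation is kept or falls under exclusion 5.
- The rule in 2.6.4 protects patients treated with intent to enrol. Intent is exactly what the grace period allows to be clarified later, so the rule does not close the gap.
- The bar on late additions does not prevent omissions or removals.
- Monitoring visits review screening (2.3.3), but no report of missed, clarified or excluded patients by arm and period is specified.

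**Step 2: reproduce the plan's sample size, to obtain a standard error.** Section 2.6.2 states: "To detect a decrease from 16.7% to 9.7% (a difference of 7%), with 80% power at 5% significance level". Its other inputs are ICC 0.025, 17 agencies and 7 periods (6 steps). A two-sided test is assumed.

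- Individually randomized size: 366 per arm, 732 in total.
- Closed-form stepped-wedge design effect with 16 patients per agency and period: [1 + 0.025(96 + 16 − 1)] / [1 + 0.025(48 + 16 − 1)] × 3(0.975) / [2(6 − 1/6)] = (3.775 / 2.575) × 0.2507 = 0.3676.
- Total: 732 × 0.3676 × 7 = 1,883. In whole agencies, 17 × 7 × 16 = 1,904, which is the stated figure.
- A Hussey-Hughes variance check gives 79.8% power.
- Implied standard error: 0.07 / (1.96 + 0.84) = 0.025.

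The sample size itself is not in question.

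**Step 3: sensitivity to net removal.** The documents give no counts, so these are assumptions. Let x be the net excess share removed from one arm and m the mortality of those removed, with p = 0.167. Observed mortality is p' = (p − xm) / (1 − x). One arm is about 1,904 / 2 = 952 patients. With m = 0.95:

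| x | Patients | p' | Shift (points) | Type I error | Power if the shift works against the planned effect |
|---|---|---|---|---|---|
| 1% | about 10 | (0.167 − 0.0095)/0.99 = 15.9% | 0.8 | 6.2% | 70% |
| 2% | about 19 | (0.167 − 0.0190)/0.98 = 15.1% | 1.6 | 9.8% | 58% |
| 3% | about 29 | (0.167 − 0.0285)/0.97 = 14.3% | 2.4 | 16.3% | 45% |

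With Φ the normal distribution function and d = shift / 0.025, type I error is Φ(−1.96 + d) + Φ(−1.96 − d). Power is Φ((0.07 − shift)/0.025 − 1.96). If all those removed die (m = 1), the shifts for 1% and 3% are 0.84 and 2.6 points, type I error is 6.3% and 17.8%, and power is 69% and 42%. These use the standard error at the planned rates. With both arms at 16.7% the standard error is 0.0277, and the type I errors in the table fall to about 5.9%, 8.9% and 14%. All are crude-difference approximations to the planned mixed model.

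**Step 4: the opposing flow.** A longer interval before the attempt also lets more patients regain circulation and enter. If a share y enters with mortality q, then p' = (p − xm + yq) / (1 − x + y). With y = x, the shift is x(m − q), which vanishes when q = m. The table therefore applies to net removal only. With no net difference between arms under the null, there is no shift.

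**The case against.** The case against is substantial on several points.

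- **The interval is not shown to differ by arm.** A reader might infer that it does from "SGAs have been associated with shorter prehospital scene times" (1.3). That sentence concerns scene time, and the remark in 2.4.2 that the technique is rapid concerns placement. Neither gives time from arrival to first attempt, and preparation stays under local protocols in the SGA arm too (2.2). The interval may differ; the documents do not establish that it does.
- **The later clock may be deliberate.** Subgroup 9 makes sense only if patients in arrest on scene can still enter. Moving every criterion to time on scene would remove that subgroup. This stands, and the fix must respect it.
- **The grace period is limited.** It covers only unclear cases, the medical director is ultimately responsible, and unidentified patients cannot be added later. A reader might infer that entry is decided with the outcome in hand. The documents show only that the outcome may be knowable by then.
- **Provider discretion is a different matter.** If the threshold falls when an agency steps, patients are added, not lost. They are in the data, indications and vital signs are abstracted in both arms (2.2), and the model adjusts for baseline covariates (2.6.1). The change is observable and at least partly adjustable. For scale, adding 10% at an assumed 5% mortality gives (0.167 + 0.10 × 0.05)/1.10 = 15.6%.

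What remains is that the two times are unreconciled, post-treatment clarification is not masked to outcome, and the patients affected are not counted by arm and period.

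**Conclusion.** The point holds as a gap that can bias the primary comparison. A reader might go further and conclude that the comparison is biased, or biased in favour of SGA. The documents do not support that: they give no counts and no time to attempt by arm. Nor is the direction fixed. Removing more arrests from the standard arm would work against SGA, later entry of patients with return of circulation would offset it, and selective enrolment could go either way.

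Under the assumed net removal of 1 to 3% of one arm at 95% mortality, the shift is 0.8 to 2.4 points, roughly one-ninth to one-third of the 7-point target. That is enough to matter for type I error or power at a standard error of 2.5 points, but it is an illustration and not an estimate. This should be fixed as a cheap improvement; the evidence does not make it a must-fix.

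**What to change.** 1. **Reconcile the times.** Bring the on-scene and intervention times in 3.3 into line with 2.2 (retention when no airway is placed) and 2.6.3 subgroup 9 (arrest at enrolment with later return of circulation). State whether patients who arrest between arrival and the airway attempt belong to the primary analysis set.
2. **Protect the entry decision from the outcome.** Require that the medical director's confirmation and any clarification rest on the EMS record up to the airway attempt, without knowledge of vital status. A patient identified as enrolled at treatment should not be removed on a later statement of intent. Masking to arm is not asked for, since arm follows from agency and period.
3. **Count and test.** Report missed, clarified and excluded patients by randomization unit and period. Pre-specify a sensitivity analysis of the primary outcome restricted to patients who meet objective indicators a to c in 3.2.

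The cost is protocol wording, a small amount of extra logging and one further analysis. It builds on records already abstracted, the existing medical director review and the screening checks in 2.3.3. No treatment changes.

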4. IRB APPROVAL AND FDA AMENDMENTS

A central IRB at the University of Pittsburgh will be utilized for the regulatory needs of this trial. All current LITES Network sites have IRBs that have experience and engagement with central IRB procedures.

The Investigator will obtain from the University of Pittsburgh Institutional Review Board (IRB) prospective approval of the clinical protocol and corresponding informed consent form(s) as well as modifications to the clinical protocol and corresponding informed consent forms.

The only circumstance in which a deviation from the current IRB-approved clinical protocol/consent form(s) may be initiated in the absence of prospective IRB approval is to eliminate an apparent immediate hazard to the research subject(s). In such circumstances, the Investigator will promptly notify the University of Pittsburgh IRB of the deviation.

The University of Pittsburgh IRB operates in compliance with FDA regulations at 21 CFR Parts 50 and 21 CFR 56, and in conformance with applicable International Conference on Harmonization (ICH) Guidelines on Good Clinical Practice (GCP).

In the event that the University of Pittsburgh IRB requires, as a condition of approval, substantial changes to a clinical protocol submitted under an FDA-accepted IDE application, or in the event of the Investigator's decision to modify the previously accepted clinical protocol, the Sponsor will submit (i.e., in advance of implementing the change) a Protocol Amendment to the IDE describing any change to the protocol that significantly affects the safety of subjects, the scope of the investigation, or the scientific quality of the study.

5. ENROLLMENT AND INFORMED CONSENT PROCEDURES

5.1 ENROLLMENT METHODS:

Potentially eligible patients will be identified prospectively by air medical and ground transport personnel trained on and familiar with the inclusion and exclusion criteria. The intervention will take place in the prehospital environment, performed by personnel trained in prehospital trauma airway management. Those who meet all inclusion and no exclusion criteria will be assigned to standard care or initial SGA based on the randomization arm currently active for that EMS agency. EMS personnel will notify site personnel of enrollments. Once notified, site personnel will review inclusions and exclusion criteria to verify eligibility and report protocol deviations.

There will be some instances where, despite the original intentions of the EMS provider, enrolled subjects will ultimately be transported to non-participating hospitals. In these instances, we will retain these subjects as enrolled and will notify them of their enrollment into the trial, but we will not anticipate receiving any data from their in-hospital encounter. 24-hour mortality may be obtained by searching public records for vital status or by other sIRB approved means.

5.2 2 INFORMED CONSENT PROCEDURES

All guidelines and requirements for notification for exception of consent for emergency research will

be followed. Patients with major trauma who require advanced airway management during or directly preceding emergency medical transport are experiencing an immediate life-threatening condition, with the patient commonly intubated, unconscious, or not responsive. In this emergent situation, it will not be possible to contact legal representatives at the time of study enrollment. Research coordinators will make every effort to contact legal representatives as soon as feasible after admission to the hospital to notify them that the subject was enrolled in a randomized trial and to attempt to obtain consent for ongoing data collection. Such notification will be in person whenever possible. Summary of these efforts will be documented. If the subject becomes competent during the study period, then he/she will be approached by research personnel for notification of enrollment and a similar provision of an opportunity to opt out from ongoing data collection.

The investigators will utilize social workers, law enforcement personnel, or any other available means to try to locate the patient's legally authorized representative. If that search is unsuccessful, a notification letter will be sent to the subject's authorized representative explaining the study and providing contact information for answering questions. The letter will be sent via a traceable method, such as registered mail or by UPS, and documentation of the addressee and date of mailing will be kept.

If the subject expires prior to being notified or obtaining consent, a letter of notification of enrollment will be sent to the subject's representative via a trackable method. This letter will contain important details describing the study, as well as provide contact information for the study team and/or the IRB to allow the family to ask questions or express concerns with the study.

If the subject recovers quickly or unexpectedly and is discharged from the hospital prior to the study team notifying and obtaining consent, a notification will be mailed to the subject via a trackable method.

